 c) The Short Physical Performance Battery (SPPB) includes the following components: 1) Timed 4-meter walk; 2) Repeated chair stand; and 3) Balance tests. For each

component, a score of 0 to 4 is assigned, with the sum of components comprising a final score

d) Grip strength: Participants will grip and hand dynamometer as hard as they can to assess handgrip strength.

The participants may be asked to wear a small triaxial accelerometer during these tests. The QTug is a small device the size of a deck of cards that is placed above each knee during the test and provides data on standing, sitting walking, and turning and allows us to better quantify fall risk and frailty in participants.

Lower extremity strength: a Biodex System 4 Pro dynamometer will be utilized to assess peak isometric hip abductor, knee extensor, and ankle plantar/dorsiflexion strength. We will use standardized protocols as described by Biodex.

Gait Biomechanics: using an instrumented walkway (GAITrite, CIR systems INC, Clifton, NJ), spatial and temporal parameters of gait and gait variability will be assessed. The GAITrite is a 25 foot portable walkway mat embedded with pressure sensors that detect steps while the subjects walks over the mat.

Lateral mobility and balance:

a) Four square step test: Participants will be timed as they step over four cones set up in a cross on the floor as a test of dynamic balance.

b) 8 Foot up and Go: Participants will be timed as they stand up from a chair, walk around a cone placed 8 feet away, and come back and sit down.

c) Functional Gait Assessment: Participants will be timed as they walk at different speeds, look in different directions and step over objects

Participants may also be asked to wear the QTug for these tests.

Anthropometrics: height, weight, and body circumference measurements

Body composition assessment:

Body Composition: Total and regional % body fat, fat mass, lean tissue mass, and bone mineral content will be determined by dual-energy x-ray absorptiometry (DXA). Bone density of the total body, including the hips will be measured using DXA. Computed tomography (CT) scans of the abdomen and thigh will quantify abdominal fat, and thigh fat and muscle. A urine pregnancy test will be completed in women of child-bearing age prior to having the CT and DXA scans. The DXA and CT scans will be performed by radiology technicians. *Body composition assessment will not be conducted at 9 months*

2 *** Describe all procedures already being performed for diagnostic or treatment purposes (if not applicable to the study, enter "N/A"):**

N/A - All study procedures will be performed for research purposes only.

3 *** Describe the duration of an individual participant's participation in the study:**

We anticipate that each volunteer's participation, if they complete all study related activities, will be approximately 24 months. However, the duration could be more or less depending on the timeframe for each phase of testing and when the group intervention classes begin and end.

4 *** Describe the amount of time it will take to complete the entire study:**

4 years

5 *** Describe any additional participant requirements:**

None

ID: VIEW4E0280585B400
Name: v2_Study Procedures

Sample Size and Data Analysis

If you uploaded a separate research protocol document in the 'Research Protocol' page, cite the applicable section and page numbers from that document in the answer boxes below.

1 * Provide the rationale and sample size calculations for the proposed target population:

SAMPLE SIZE CALCULATIONS were determined for the physical outcomes. Perera and colleagues proposed that an improvement of 19-22 meters on the 6 minute walk test (6MWD) would be clinically meaningful and an increase of 47-49 meters would be considered substantial (72). In our prior studies in subjects with impaired mobility, exercise increased 6MWD 10 to 30%. In our preliminary studies in obese mobility limited Veterans enrolled in Gerofit, the 6MWD increased by 15% (57 +/- 60 m) and the number of chair stands performed by 19%. We anticipate greater improvements with weight loss + MMBI on the order of 30 to 50 M greater improvement in MMBI + weight loss versus MMBI only. Using lower estimates, if the true difference in mean response of matched pairs is 30 +/- 50 meters, we will need to study 45 subjects in each group to be able to reject the null hypothesis with two-sided power of 0.8 and Type I error probability of 0.05. We previously reported that an exercise intervention in middle aged and older overweight and obese men increased VO2peak (L/min) by 17% with no change with weight loss (50). The study by Villareal et al. reported a 17% improvement in VO2peak in the combined group versus about 6% in the diet group. To detect a 15% difference in VO2peak between groups with a power of 0.80 and a p-value <0.05, we would need to enroll 41 subjects per group, which is close to the sample size required for the 6MWD. On a percentage basis we anticipate that there will be even more substantial improvements in lateral mobility and balance as assessed by the four square step test (FSST) than that observed for the change in usual gait speed or 6MWD. In our preliminary data, the MMBI decreased the time to complete the FSST by 24%, with the greatest improvement in the frailest subjects. Therefore, fewer subjects might be required to demonstrate a difference in the improvement in balance between groups.

We will enroll 60 subjects. Typical attrition rates are 20-25%, primarily due to the development of non-study related medical problems. This will result in 45 completers. If a greater than anticipated number of subjects fail to complete the study, we will enroll additional subjects.

2 * Provide the plan for data analysis. Include in the description the types of comparisons that are planned (e.g., comparison of means, comparison of proportions, regressions, analysis of variance, etc.), which is the primary comparison/analysis, and how the analyses proposed will relate to the primary purposes of the study:

All comparisons of primary and secondary outcomes will be performed in accordance with intention-to-treat principles. As with all clinical trials, it is anticipated that there may be missing data elements. Multiple imputation will be used to account for missing values. Our first analyses will be exploratory designed to identify extreme values. Extreme values will be checked to make sure they are not the result of data entry errors. Statistical significant will be a two-sided alpha of 0.05.

Specific aim 1. Our study will compare the effects of MMBI+nutrition on mobility and functional performance in older obese Veterans with walking impairment requiring a walking assistive device. We will use repeated measures ANOVA to model the time-course of our outcome measures. We will use AICC (a modification of Akaike's Information Criterion) to choose between three covariance structures that can account for the serial auto-correlation of our subject's data.

Specific aim 2. Using DXA and CT scans, we will quantify total muscle mass and cross-sectional muscle area at numerous levels at baseline, 3, 6, 12, and 24 months. At baseline there should be a direct correlation between total muscle, ASMI, cross-sectional muscle mass and the indices of functional performance. With the exercise intervention, we expect that there will be small, but significant increases in lean muscle mass and ASMI (ANOVA). This change may be beyond the limits of detection of the DXA. Assessment of cross-sectional muscle area by CT scan may provide a more sensitive measurement of muscle mass than DXA. The relationship between muscle mass, strength, and functional performance at baseline and after the intervention will be examined. Body composition (% fat, fat-free mass, regional distribution of body fat) may change with intervention. Regression analyses will be used to determine whether the change in 6MWD, and other mobility parameters are related to the change in muscle mass (DXA, CT scan) or muscle strength (Biodex) with intervention. We will also perform multivariate modeling. It is important to dissect how much of the improvement in mobility after intervention is attributable to changes in fitness, economy of gait, and other factors such as balance, and strength. The functional measures in combination with the assessments of muscle mass by DXA will also allow us to determine the prevalence of sarcopenia using recently published NIH guidelines.

Specific Aim 3. We will examine the impact of the intervention on patient reported measures of function and disability using the LLFDI. We will compare LLFDI total scores and subscale scores using an analysis plan similar to that for aim 1. We will also examine the correlations between the self-reported measures and performance measures to provide further evidence of validity and reliability.

ID: VIEW4E02806052800
Name: v2_Sample Size and Data Analysis

Sharing of Results

1 * Describe whether results (study results or individual subject results, such as results of investigational diagnostic tests, genetic tests, or incidental findings) will be shared with subjects or others (e.g., the subject's primary care physicians) and if so, describe how it will be shared:
Results which have clinical relevance will be shared with participants, and with their permission, their primary care providers.

ID: VIEW4E02808CBD800
Name: v2_Sharing of Results

Psychological/Behavioral/Educational Methods & Procedures

You indicated on the "Type of Research" page that your study involves a psychological/behavioral/educational method or procedure such as a survey, questionnaire, interview, or focus group.

1 * Select all behavioral methods and procedures which apply to this study:

- Surveys/questionnaires
- Key informant or semi-structured individual interviews
- Focus groups or semi-structured group discussions
- Audio or video recording/photographing
- Educational tests or normal educational practices (education instructional strategies, techniques, curricula, or classroom management methods)
- Individual or group behavioral observations
- Psychosocial or behavioral interventions
- Neuropsychological or psychophysiological testing
- Deception
- Other psychosocial or behavioral procedures

ID: VIEW4E09418F57800

Name: v2_Psychological/Behavioral/Educational Methods and Procedures

Surveys/Questionnaires

You indicated that this study involves surveys and/or questionnaires.

If you uploaded a separate research protocol document in the 'Research Protocol' page, cite the applicable section and page numbers from that document in the answer boxes below.

1 * List all questionnaires/surveys to be used in the study, including both standardized and non-standardized assessments:

The CHAMPS Questionnaire
 ADL/IADL
 Late Life Function and Disability Instrument
 Mini-Mental State Examination (MMSE)
 Montreal Cognitive Assessment (MoCA)
 Mini Nutritional Assessment (MNA)
 Screen II
 Beverage Questionnaire (BEV-Q 15)
 Newest Vital Sign
 Pittsburg Sleep Quality Index (PSQI)
 MOVE 11
 Weight Loss and Barriers Questionnaire

2 * Upload a copy of all questionnaires/surveys:

Name	Created	Modified Date
BEV-Q 15(0.02)	12/9/2016 3:02 PM	9/21/2017 8:48 AM
Weight Loss and Barriers Questionnaire(0.01)	7/7/2017 8:22 AM	7/7/2017 8:22 AM
MOVE11(0.01)	12/9/2016 3:14 PM	12/9/2016 3:14 PM
Pittsburgh Sleep Quality Index(0.01)	12/9/2016 3:03 PM	12/9/2016 3:03 PM
Newest Vital Sign(0.01)	12/9/2016 3:02 PM	12/9/2016 3:02 PM
MNA(0.01)	12/9/2016 3:01 PM	12/9/2016 3:01 PM
SCREEN II(0.01)	12/9/2016 3:01 PM	12/9/2016 3:01 PM
MoCA Test.pdf(0.01)	5/27/2016 1:01 PM	5/27/2016 1:01 PM
LLFDI disability questionnaire(0.01)	5/27/2016 1:00 PM	5/27/2016 1:00 PM
LLDFI Function Questionnaire(0.01)	5/27/2016 12:59 PM	5/27/2016 12:59 PM
MMSE.pdf(0.01)	4/26/2016 3:24 PM	4/26/2016 3:24 PM
CHAMPS Questionnaire.pdf(0.01)	4/26/2016 3:23 PM	4/26/2016 3:23 PM
ADLs_IADLs questionnaire.pdf(0.01)	4/26/2016 3:23 PM	4/26/2016 3:23 PM

3 * What is the total length of time that each survey is expected to take?
 MMSE will only be performed at screening. MNA, SCREEN II, and Weight Loss and Barriers and MOVE 11 will only be given at baseline will take approximately 20 minutes in total. It will take approximately 5 -10 minutes per survey at each time point. The surveys are a tertiary aim of this protocol. To reduce subject burden some surveys may not be completed at all research testing time points.

4 * Are any of the questions likely to cause discomfort in participants or cause harm if their confidentiality were breached? (i.e., Illegal activities)

Yes No

5 * Do any questions elicit information related to the potential for harm to self or others?

Yes No

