Older obese adults suffer disproportionately from walking mobility limitations. Sedentary, obese older adults are at an increased risk for having or developing difficulties with mobility. These individuals are often excluded from studies due to their advanced mobility limitations. A number of studies have compared the effects of weight loss alone, exercise alone, or weight loss in combination with exercise on functional performance in older adults, but none of the studies have specifically targeted subjects who use walking assistive devices. The purpose of this study is to test the effects of a 3 month multi-modal balance intervention (MMBI) with a nutrition program with optional retention till 24 months on fitness, functional performance, mobility, and muscle mass. The results of this study will lead to new and more effective interventions that could reduce disability, fall risk, injury-related hospitalization and death in older Veterans.

ID: VIEW4E02805CF7000
Name: v2_Lay Summary

Justification, Objective, & Research Design

If you uploaded a separate research protocol document in the 'Research Protocol' page, cite the applicable section and page numbers from that document in the answer boxes below.

- 1 *** Describe the purpose, specific aims, or objectives of this research. State the hypothesis to be tested:**
 Specific aim 1: Examine the effects nutrition + multimodal balance intervention (MMBI) on mobility and functional performance in the following outcomes:
 a. 6 minute walk (primary outcome)
 b. Other physical performance outcomes: 6MW with economy of gait, gait rite, four square step test, 8 foot up and go, short physical performance battery, grip strength, lower extremity strength
 Specific aim 2: Examine the relationship between muscle mass, strength, and functional performance using DXA and CT scans to quantify body composition.
 Specific aim 3: Examine the impact of the intervention on patient reported measures of function and disability using the Late Life Function and Disability Instrument (LLFDI).
- 2 *** Discuss the research design including but not limited to such issues as: probability of group assignment, potential for subject to be randomized to placebo group, use of control subjects, etc.:**
 All subjects will now receive MMBI and nutrition (combined intervention). Weight loss will be a covariate in the analyses.
- 3 *** Describe the relevant prior experience and gaps in current knowledge. Describe any relevant preliminary data:**

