 Seventeen older (age >70 years) adults with a history of falls were recruited for a preliminary study of our MMBI. Subjects exercised 3 times/week for 16 weeks in our gymnasium followed by a four-month long home exercise regimen (adapted from the VISION 8 program) after completion of the center-based portion of the intervention. Sixteen out of 17 individuals completed all portions of the study with > 90% adherence in the 16 who completed the study. Six of the 16 fell at least once during the 4 months of the home-based phase of the study, and an additional six subjects reported at least 1 near fall. These falls and near falls did not occur during the exercise, but rather during normal daily activities. Four-square times in those who fell were significantly slower (12.7 +6.5 seconds) than in those who did not fall (6.0 + 2.1 seconds, p < 0.01). Notably, however, the slower individuals also had the greatest improvement with the intervention. After 16 weeks of center-based exercise, MMBI scores on the functional gain assessment increased by 12% and the time to complete the four-square test decreased by 24%, with even greater improvements of 40-50% for individuals whose function was most impaired at baseline. Distance covered during the six minute walk increased by 5% (p < 0.04). Maximum weight lifted during a leg press increased demonstrating significant improvements in lower extremity strength. Importantly these improvements were maintained after the four-month home-based exercise program. The subjects in this study differ from those we propose to study as the primary enrollment criteria was a history of falls, not obesity. In addition, there was no requirement that they use walking assistive devices. Nevertheless, these findings demonstrate that our multimodal intervention can be performed safely in an at risk population and improves multiple physical performance domains.
 GEROFIT cross-sectional data

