 We performed assessments of physical functioning in 24 older (> 65 years) Veterans at risk of functional and mobility decline based on their use of walking assistive devices enrolled in the GEROFIT clinical demonstration project. All of the subjects had performance-based evidence of impaired mobility. Overall the subjects had slow gait speed, poor lateral mobility and balance on the four square step test (FSST), poor endurance on the 6 minute walk test and reduced lower extremity proximal strength on the chair stands. Many of the Veterans scored below the 5th percentile on many of these measures and >50% had SPPB scores < 9. Impact of 3 months of GeroFit on functional performance in older obese Veterans: In this revised grant we provide preliminary data in 16 obese (BMI 35.8 + 5.7) older (71 + 4 years) Veterans with SPPB scores < 10 (8.5 + 1.7, mean + SD) indicative of lower extremity functional impairment who completed 3 months of GeroFit. On average these subjects had 10 medical problems and were taking 15 medications per day. After 3 months their SPPB improved from 8.5 + 1.7 to 9.56 + 2.1, the number of chair stands performed in 30 seconds increased from 7.5 + 3.7 to 8.9 + 5.4, four square step test (FSST) time an index of fall risk and lateral mobility decreased (improved) from 14.0 + 5.0 to 13.0 + 4.2 seconds and 6 minute walk distance increased from 363 + 118 yards to 418 + 122 yards. On average weight did not change in these Veterans. The exercise intervention proposed in this study will be of longer duration, with greater individualized attention with a more customized exercise progression than that employed in GeroFit.
- 4 *** Provide the scientific or scholarly background, rationale, and significance of the research and how it will add to existing knowledge:**
 Depending upon the criteria employed, it is estimated that >11 million older adults, or approximately one-third of non-institutionalized older adults have impaired mobility and >4 million older adults use walking assistive devices (1,2). It is well established that performance-based indices of impaired mobility such as slow gait speed, inability to perform the 400 m walking test and poor distance covered during the 6 minute walk test are predictive of increased mobility limitation, mobility disability, cardiovascular mortality and death.¹¹⁻¹⁴

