Obesity, low cardiovascular fitness and slow gait speed is associated with increased morbidity and mortality. Few studies have examined the effect of weight loss and exercise rehabilitation on functional status in older obese individuals with mobility limitations who use walking assistive devices as these individuals often excluded from studies. There is limited evidence from intervention studies that weight loss alone or weight loss in combination with exercise rehabilitation can increase mobility and lower extremity function in older obese subjects. Preliminary studies in our group demonstrate that a novel progressive group multimodality balance intervention (MMBI) that focuses on lateral and diagonal movements, lower extremity and core muscle strengthening and dynamic obstacle negotiation can improve fitness, balance, gait and strength in older adults at high risk for functional decline. While we believe that both MMBI only and nutrition + MMBI training will improve gait and balance, we hypothesize that nutrition + MMBI will result in larger improvements in fitness, gait, balance and lower extremity strength. This intervention will potentially reduce the risk for institutionalization, reduce the cost of fall associated morbidity and mortality in older veterans by improving gait and balance. This research directly benefits Veterans as it may lead to new and effective interventions that could improve walking mobility, reduce fall risk, reduce injury-related hospitalization and death in older Veterans. The nutrition + MMBI is readily exportable to the community and with minimal resources could be widely implemented at other VAs as part of standard of care.

3 * Describe how the potential risks to participants are reasonable in relationship to the potential benefits:

We believe that the benefits associated with this study will exceed the risks, thereby resulting in a low risk:benefit ratio for any participant in the study.

4 * Describe the alternatives to participation in this study. If there are no alternatives, state that participation is voluntary and the alternative is not to participate. For intervention studies, describe appropriate alternative clinical procedures or courses of treatment available to subjects.

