3 * **Confirm** - you have read the above information and understand that in addition to the IRB Protocol form, you will fill out and submit the IBC Submission form :

Yes No

ID: VIEW4E1AF91ED4C00
Name: v2_Institutional Biosafety Committee Review Required

VA-Specific Criteria

1. * **What is the relevance of this research to the mission of VA and the Veteran population that it serves*?**
This study is particularly relevant to the older veterans as the prevalence of obesity continues to rise, placing older Veterans at increased risk for disability, morbidity and mortality. Even modest improvements in physical functioning in this older population with dysmobility may significantly impact on their ability to live independently in the community and reduced ADL dependence and potentially decrease institutionalization. This research directly benefits Veterans as it may lead to new and more effective interventions that could reduce disability, reduce fall risk, and reduce injury-related hospitalization and death. This nutritional and multimodal exercise intervention is readily exportable to the community and with minimal resources, could be widely implemented at other VAs as part of clinical care as an enhancement to MOVE!. Thus, the proposed interventions are likely to have real world impact on Veterans and their health.

2. * **Describe who will be enrolled in this study:**
 - Non-veterans will be enrolled in this study
 - Only veterans will be enrolled in this study
 - Veterans and Non-veterans will be enrolled in this study

- 2.1. * **If non-veterans will be enrolled in this study, provide a description of non-veterans who will be enrolled (For example: community members, family members/caretakers of Veterans, clinicians/caregivers to Veterans, etc.):**
not applicable

- 2.2. **If non-veterans will be enrolled in this study, provide a substantive justification** for the enrollment of non-veterans in this research:**

- 2.3. * **If this is a VA-funded study, was the use of non-veterans discussed within your merit award proposal?**
 - Yes
 - No
 - N/A

*

http://www.va.gov/about_va/mission.asp

VA Mission Statement

To fulfill President Lincoln's promise "To care for him who shall have borne the battle, and for his widow, and his orphan" by serving and honoring the men and women who are America's Veterans.

VA Core Values

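### With every subject on MMBI plus nutrition, the Aim 1 analysis can show only a within-group change in 6MWD; it cannot test the retained hypothesis that nutrition adds to MMBI

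*Combined protocol and SAP*

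**What the plan says.** **Design and analysis.** Justification, Objective, & Research Design, item 2, says "All subjects will now receive MMBI and nutrition (combined intervention" and adds that weight loss will be a covariate. Item 1 makes the 6-minute walk the primary outcome. For Aim 1, Sample Size and Data Analysis, item 2, says "We will use repeated measures ANOVA to model the time-course of our outcome measures" and "Statistical significant will be a two-sided alpha of 0.05". It names no control, benchmark or margin, and it does not write out a null hypothesis.

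**Comparative statements that remain.** Potential Benefits and Alternatives, item 2, sets MMBI only beside nutrition + MMBI and continues: "we hypothesize that nutrition + MMBI will result in larger improvements in fitness, gait, balance and lower extremity strength". Sample Size and Data Analysis, item 1, expects 30 to 50 m more improvement with weight loss added than with MMBI only, and takes 30 ± 50 m to reach 45 subjects in each group. The Lay Summary and VA-Specific Criteria, item 1, look ahead to more effective interventions; the latter says "it may lead to new and more effective interventions that could reduce disability". The tear-off flyer in Advertising Detail still describes exercise versus exercise plus weight loss.

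**Exercise data in the plan.** Justification, item 3, reports on 16 obese Veterans who completed 3 months of GeroFit: "6 minute walk distance increased from 363 + 118 yards to 418 + 122 yards", with no mean change in weight. Sample Size and Data Analysis, item 1, gives the gain as 15%, 57 ± 60 m. For the MMBI pilot in older adults with a history of falls, item 3 says "Distance covered during the six minute walk increased by 5" per cent.

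**The concern.** A one-arm time-course model has only a time effect to test. The natural null is no change in 6MWD from baseline. That null is inferred here, because the plan does not state it. Rejecting it says that walking distance changed while subjects were on the combined programme. It says nothing about what nutrition contributed, because no group goes without it.

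The plan's own figures make the gap concrete. Both exercise data sets show 6MWD rising, and in GeroFit it rose with mean weight unchanged. A positive primary result is therefore what one could see if nutrition added nothing. If the retained hypothesis is read together with a significant p-value, the trial could be reported as showing a larger benefit from the combination, a claim that no planned analysis tests. Restating the sample size for a within-group change would not cure this, because the null would stay the same.

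**Working it through.** **1. The plan's own sample size.** Inputs from Sample Size and Data Analysis, item 1: difference 30 m, SD 50 m, two-sided alpha 0.05, power 0.80.
- Two-sample normal formula: n per group = 2 × (1.960 + 0.842)² × 50² / 30² = 43.6, so 44. The t-test version gives 44.6, so 45. The plan's 45 per group is reproduced.
- The matched-pairs wording in the same sentence does not reproduce it: a paired t-test needs 24.
- Attrition of 25%: 60 × 0.75 = 45 completers in the one remaining arm.

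The figure of 45 is thus the size of one arm of a two-arm comparison that the design no longer contains.

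**2. The exercise gains in metres.**
- GeroFit: 418 − 363 = 55 yards; 55 × 0.9144 = 50.3 m. On a baseline of 363 × 0.9144 = 331.9 m this is 15.2%, which fits the 15% in the sample-size section. A gain of 57 m on that baseline would be 17.2%. The two figures need reconciling.
- Uncertainty with 16 subjects, reading ± 60 m as the SD of change: SE = 60/√16 = 15 m. The 95% limits around 57 m are 57 ± 2.131 × 15, or 25 to 89 m.
- MMBI pilot: 5% × 331.9 = 16.6 m. This is an assumption. The pilot's own baseline distance is not given, so the GeroFit baseline is borrowed.

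**3. Chance that a test against zero is significant.** One-sample t-test on the 3-month change, n = 45, two-sided alpha 0.05, noncentrality = gain / (SD/√45). At SD 60 the standard error is 60/√45 = 8.94 m, so the noncentrality is 5.62 at 50.3 m, 2.80 at 25 m and 1.86 at 16.6 m. The SD of 60 m is the GeroFit figure and 50 m is the planning value; 80 and 100 m are assumed to show the range.

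| True mean gain | SD 50 | SD 60 | SD 80 | SD 100 |
|---|---|---|---|---|
| 57 m | >99.99% | 99.999% | 99.7% | 96.2% |
| 50.3 m | >99.99% | 99.98% | 98.5% | 91.0% |
| 25 m | 90.7% | 78.0% | 53.6% | 37.5% |
| 16.6 m | 58.6% | 44.2% | 27.5% | 19.3% |

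The smallest observed mean gain that reaches significance is 2.015 × 8.94 = 18.0 m at SD 60, or 15.0 m at SD 50.

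**4. Limits of the calculation.** The planned analysis uses several visits, intention-to-treat and multiple imputation. The one-sample t-test is a stand-in for its baseline-to-3-month contrast. The percentages show scale; the point that one arm cannot test a between-regimen difference does not depend on them.

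**The case against.** The strongest reply is that the test fits the question. Aim 1 sets out to examine the effects of the combined programme, and the background (Justification, item 4) asks whether obese older adults who use assistive devices can improve their mobility. Both are change-from-baseline questions. The more-effective wording sits in a lay summary and a relevance answer, names no comparator and is aspirational. The hypothesis in the benefits section looks like text left over from a two-arm design. All of this stands: the analysis of Aim 1 is not wrong for Aim 1 as written. What remains is that an explicit comparative hypothesis, and a sample size built on it, are still in the current text with nothing to test them.

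A reader might go further and infer that a programme no better than current exercise would pass almost surely. The documents do not support that in general:
- The 99.98% belongs to the GeroFit point estimate from 16 completers. At about the lower confidence limit around 57 m it is 78%.
- The comparator that the documents name is MMBI only, where the figure is 44% to 59% and rests on a borrowed baseline.
- GeroFit is a different programme, never set as comparator. The documents report no mean weight change in it; they do not say whether it had nutrition content.
- The MMBI pilot enrolled people with a history of falls, who trained three times a week for 16 weeks. The current MMBI is weekly or every other week.
- The Recruitment section draws on GeroFit participants, whose study baselines may already contain some of that gain. Their share is not stated.

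Nor does the weight-loss covariate supply the missing comparison. Weight loss within one arm is not randomised and arises after baseline, partly as a result of the intervention.

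**Conclusion.** The concern holds in a limited form. The planned primary analysis supports a statement that 6MWD changed from baseline, and no more. It cannot test whether nutrition + MMBI does better than MMBI only, and a significant result does not show that the programme is more effective than existing exercise.

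The size depends on what exercise alone would achieve in these subjects: significance about 99.98% of the time at 50.3 m, 78% at 25 m and 44% at 16.6 m, for 45 completers and SD 60 m (59% for the last at SD 50). These figures assume a null of zero change, ± 60 m as an SD, and 5% applied to another cohort's baseline. Even the lowest of them is far above the nominal 5%. The defect lies in the claims attached to the analysis, and wording can correct it.

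**What to change.** 1. In Aim 1 and in the Aim 1 analysis text, state that the primary analysis supports only a within-group change in 6MWD from baseline, and report the 3-month mean change with its 95% CI. With 45 completers the half-width would be about 18 m at SD 60 or 15 m at SD 50.
2. In Potential Benefits and Alternatives, item 2, withdraw the comparative hypothesis as a conclusion of this trial. Qualify the more-effective wording in the Lay Summary and VA-Specific Criteria, and bring the flyer into line.
3. Reconcile the GeroFit gain of 50.3 m (from yards) with the 57 m in the sample-size section.
4. If the GeroFit gain is shown beside the trial result, label it descriptive, non-randomised context: 16 completers, a different programme, and possible overlap with the recruitment pool. Rest no claim of benefit beyond existing exercise on it. An interval for the difference would not control confounding or completer selection, and 45 versus 16 subjects at SD 60 gives only about 39% power for a 30 m advantage.

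This costs a few sentences and a weaker headline claim; no extra subjects or visits are needed. If the sponsor wants the comparative claim, a concurrent MMBI-only group is required. At the plan's own 30 m and SD 50 that means 2 × 45 = 90 completers, or 90/0.75 = 120 enrolled at 25% attrition.
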